#### **10.1.2. Adverse Events**

Each AE and SAE term will be recorded as a verbatim term on the case report forms (CRFs). All AEs and SAEs will be coded by primary system organ class (SOC) and mapped to a preferred term using the MedDRA dictionary (version 26.0 or higher). The investigator will assess AE severity and relationship to the study treatment.

All AEs will be listed. However, only treatment emergent adverse events (TEAEs) will be included in the AE summaries. A TEAE is defined as any AE with an onset date on or after the first study treatment dosing date. In addition, any AEs that the investigators deem to be treatment related, regardless of onset date, will also be considered TEAEs and will be included in the AE summaries.

For the purpose of calculating treatment emergence and inclusion in summary tables, incomplete onset dates will be imputed using the method described in Appendix A.

AEs will be summarized by the number and percentage of subjects in each primary SOC and preferred term. Subjects will be counted only once for each primary SOC and each preferred term. Summary tables of AEs by primary SOC, preferred term and severity will be provided. If a subject has more than one AE coded to the same preferred term, the subject will be counted only once for that preferred term by using the event with the highest severity. Similarly, if a subject has more than one AE within a primary SOC category, the subject will be counted only once in that SOC category by using the event with the highest severity. AEs by primary SOC, preferred term and relationship to study drug will be provided as well. If a subject has more than one AE coded to the same preferred term, the subject will be counted only once for that preferred term by using the most related event. Similarly, if a subject has more than one AE within a primary SOC category, the subject will be counted only once in that primary SOC category by using the most related event. In addition, serious adverse events (SAEs) by primary SOC and preferred term will be provided. Deaths and SAEs will be summarized similarly to AEs. All adverse event tables will also include the total number of events, counting multiple events per subject.

In the AE summary, preferred terms within each SOC will appear in alphabetical order.

Frequencies for deaths and hospitalizations will also be summarized by treatment group and overall.

All information obtained on AEs will be displayed by treatment group.

The number (and percentage) of subjects with treatment emergent AEs (events started after the first dose of study medication or events present prior to start of treatment but increased in severity based on preferred term) will be summarized in the following ways:

- AEs by primary System Organ Class (SOC) and Preferred Term
- AEs rated to have relationship to study drug by SOC and Preferred Term
- AEs by primary SOC, Preferred Term, and maximum severity
- SAEs by SOC and Preferred Term
- SAEs rated to have relationship to study drug by SOC and Preferred Term
- Deaths by SOC and Preferred Term
- AEs leading to discontinuation of a study drug by SOC and Preferred Term
- AEs leading to dose adjustment or interruptions of a study drug by SOC and Preferred Term
- Infections by type of infection (viral, bacterial, fungal, and others) and microorganism of infection
- Serious infections by type of infection and micro-organism of infection
- AEs by standardized MedDRA query (SMQ) levels (broad and narrow search)
- AEs by SMQ and Preferred Term (broad and narrow search)

Separate summaries will be provided for study medication related AEs, death, SAEs, other significant AEs leading to discontinuation and AEs leading to dose adjustment.

All AEs will be presented in individual by-subject data listings. Listings of any subject experiencing TEAEs related to study drug, and an SAE will be provided separately.

#### **10.1.3. Laboratory Assessments**

Descriptive statistics (mean, SD, minimum, median and maximum) of quantitative laboratory variables, including change from baseline, will be generated by visit. Summary of change from baseline in liver function tests, renal function tests, and other clinical chemistry and hematology laboratory tests will be provided for the Safety Set. Shift tables describing changes from baseline based on the clinical notable criteria will be presented.

Results of laboratory tests will be presented in listings.

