#### 4.5.1.4 Other Hypothetical Risks

# **Renal Dysfunction**

In two renal transplant tolerance studies, NKD03/ITN010ST (n=5) and ITN036ST (n=5), a transient, acute kidney injury (AKI)-like syndrome was reported in a majority (9/10) of patients early in the post-transplant course. The syndrome was associated with recovery of host hematopoietic cells and rapid loss of donor chimerism at approximately two weeks post-transplant and is better described as Chimeric Transition Syndrome (CTS). Patients in these two trials received siplizumab (0.6 mg/kg MEDI-507 on Days -1, 0 and 1) in combination with a non-myeloablative, cyclophosphamide-based, conditioning regimen, thymic irradiation and rituximab pre- and post-transplant. Patients also received a combined haploidentical bone marrow cell infusion to induce transient chimerism and a renal allograft from the same donor on Day 0.

Patients with CTS presented with a significant increase in serum creatinine (SCr) with onset around post-transplant day 10-14 that peaked (SCr range 3.5 to 15.4 mg/dL) between days 10-20; resolving by day 30. Renal biopsies taken during the CTS event were negative for T-cell mediated rejection but showed capillary endothelial injury with cellular infiltrates (CD8+/CD68+ cells) in the peritubular and glomerular capillaries.

Overall, 78% (7/9) of patients recovered normal renal function following the CTS event; 3 patients recovered with minimal intervention (corticosteroid pulse) while 4 patients required treatment (Intravenous Immunoglobulin (IVIG), ATG and/or plasma exchange). The two remaining patients failed to recover full renal function; this included one patient who lost their graft at day 10 due to severe antibody mediated rejection as well as a patient who presented with subsequent CNI toxicity and later progressed graft loss associated with thrombotic microangiopathy at Month 7.

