### 4. STUDY DESCRIPTION

#### 4.1. Study Objectives and Endpoints

Objectives	Endpoints
Primary	

To assess the safety, tolerability, pharmacokinetics (PK), and pharmacodynamics (PD) of siplizumab compared to rabbit anti-thymocyte globulin (rATG), in de novo renal transplant recipients over 12 months post-transplant.

	

Adverse events

Serious adverse events

Clinically significant changes in clinical chemistry, hematology, vital signs, serology

Siplizumab PK

PK-PD relationship

Secondary	

To measure changes in peripheral lymphocyte immunophenotype

To measure the time-course and duration of Siplizumab induced lymphocyte depletion and time to recovery

To measure peripheral CD2-receptor occupancy following Siplizumab administration over time

To assess the incidence of treated biopsy proven acute rejection (tBPAR) at 12 months

To assess the incidence of treatment emergent de novo, donor specific antibodies (DSA) at 12 months

To assess the incidence of antibody mediated rejection at 12 months

To assess renal function via eGFR using the Modification of Diet in Renal Disease (MDRD) equation at Months 3, 6, 12 or EOS

	

Immunophenotyping via FACS

Lymphocyte counts

CD2-receptor occupancy (RO)

Incidence of tBPAR

de novo DSA/anti-HLA antibody measurement

incidence of AMR

eGFR via MDRD

Exploratory

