### **8.2. Definition of Baseline**

Unless otherwise stated, the last observed measurement prior to or on the date of first study medication will be considered the baseline measurement.

For eGFR analysis (See Section **Error! Reference source not found.**), the baseline will be based on the Week 4 assessment.

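### The creatinine and BUN change and shift tables in SAP 10.1.3 are referenced to a pre-transplant (at latest Day 0) value, so they do not reliably show a post-transplant rise within subjects by arm

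*SAP*

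**What the plan says.** SAP 8.2 sets the default baseline: "Unless otherwise stated, the last observed measurement prior to or on the date of first study medication will be considered the baseline measurement". It makes one exception, for the eGFR analysis, where "the baseline will be based on the Week 4 assessment"; the section cross-reference attached to that exception does not resolve.

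SAP 10.1.3 names no baseline. It provides a "Summary of change from baseline in liver function tests, renal function tests, and other clinical chemistry and hematology laboratory tests" for the Safety Set, and adds that "Shift tables describing changes from baseline based on the clinical notable criteria will be presented". It also states: "Descriptive statistics (mean, SD, minimum, median and maximum) of quantitative laboratory variables, including change from baseline, will be generated by visit". Listings follow.

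SAP 4.1 lists "Clinically significant changes in clinical chemistry, hematology, vital signs, serology" among the endpoints for the primary objective. Protocol 8.4.4.2 puts creatinine and urea/BUN in the chemistry panel. Protocol 3.1 makes Day 0 the day of both transplant and first dose, and Protocol 6.2.6 requires the first siplizumab infusion to be complete before the graft is revascularized.

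Under Renal Dysfunction, Protocol 4.5.1.4 describes an early syndrome in 9 of 10 patients in two earlier siplizumab tolerance studies. It began around Day 10 to 14, with creatinine "that peaked (SCr range 3.5 to 15.4 mg/dL) between days 10-20", and resolved by Day 30.

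**The concern.** For most laboratory tests, a baseline at first dose is the natural reference. In a kidney transplant recipient it is not a natural reference for creatinine or BUN, because the value comes from the failed native kidneys and the graft then changes it greatly for reasons unrelated to the induction agent. A later graft injury can lift creatinine well above the level the graft had reached and still leave it below the pre-transplant value. The change table then prints a negative number. A shift table with a single high cut-off prints high to high.

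The Week 4 exception for eGFR suggests that this was recognised for eGFR. It leaves creatinine, from which eGFR is calculated, on the default. It also does not serve the early period: the described syndrome peaks on Days 10 to 20, and a change measured from Week 4 starts after that.

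At stake is whether the specified summaries for a primary endpoint let a reader compare the arms on within-subject deterioration of the graft in the first weeks.

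**Working it through.** **1. Which baseline applies.** SAP 10.1.3 states none, so SAP 8.2 governs. Its only exception is the eGFR analysis. Creatinine and BUN therefore take the last value before, or on the date of, first dose. Because the first siplizumab infusion ends before revascularization, this is a pre-transplant value unless a later sample from the same date is used. Footnote (e) of the Schedule of Assessments has chemistry drawn daily in hospital, so a post-operative Day 0 sample is possible. Hence pre-transplant, or at latest Day 0.

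**2. No planned figure to reproduce.** The study is descriptive, and the SAP gives no number on this point.

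**3. Inputs.** Documented: peak creatinine 3.5 to 15.4 mg/dL (Protocol 4.5.1.4). Assumed, because the documents are silent: pre-transplant creatinine over a range, and a stable graft value of 1.3 mg/dL for illustration.

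**4. Sign of the change.** Change = peak − baseline (mg/dL).

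| Peak | Pre-transplant 4 | Pre-transplant 8 | Pre-transplant 12 |
|---|---|---|---|
| 3.5 | −0.5 | −4.5 | −8.5 |
| 6 | +2.0 | −2.0 | −6.0 |
| 15.4 | +11.4 | +7.4 | +3.4 |

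The change is negative exactly when the peak is below the pre-transplant value. The top of the documented range shows as a rise in every column.

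**5. How often.** With peaks uniform over 3.5 to 15.4 and one fixed pre-transplant value b, the share read as a fall is (b − 3.5)/(15.4 − 3.5). For b = 6, 8 and 10 this is 2.5/11.9 = 21%, 4.5/11.9 = 38% and 6.5/11.9 = 55%. Letting the pre-transplant value vary between subjects (lognormal with those means, log-SD 0.35, clipped to 2 to 20) gives 21%, 38% and 53%, with mean change of about +3.4, +1.5 and −0.5 mg/dL. At an assumed mean of 4 the share is 7%.

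**6. Size of the change.** Take pre-transplant 8, graft 1.3 and peak 6. From the SAP baseline the change is 6 − 8 = −2.0; from the graft's own level it is 6 − 1.3 = +4.7. In an arm of 8 with two such subjects, the mean at that visit is (6 × 1.3 + 2 × 6)/8 = 2.475. That is a mean change of −5.5 from the SAP baseline and +1.2 from the post-transplant reference. With no injuries the figures are −6.7 and 0. Where the change is positive, it still understates the rise whenever the graft's best value was below the pre-transplant value.

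**7. Shift table.** If one high cut-off lies below both values, every case in step 4 is high to high. Criteria that are graded or relative to baseline could register the largest peaks: 15.4/8 = 1.9-fold and 15.4/4 = 3.9-fold. The available text does not define the clinically notable criteria.

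**The case against.** The strongest reply is that little is lost.

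- A subject's baseline is a constant. In a subject with creatinine 8.0 before transplant, 1.3 on Day 7 and 3.5 on Day 14, the change goes from −6.7 to −4.5, so the 2.2 mg/dL rise appears in full between visits. This stands for one subject followed across rows. A by-visit arm summary does not join the rows within subjects, and peaks at different times blur.
- All arms are transplanted and treatment is randomized within cohort, so the transplant-related fall is common to the arms in expectation and a difference in mean change survives. This stands. A reader might infer that the transplant effect cancels or reverses the arm comparison; it does not, though variation in pre-transplant values adds noise with 8 subjects per arm.
- Observed values by visit with their maximum, laboratory listings, adverse events, graft loss and eGFR by visit are all reported. With 24 open-label subjects, listings can be read directly. This stands, and it rules out any claim that injury is concealed.
- SAP 12.4.2, Serum Creatinine, appears in the contents but its text is redacted. It may set another baseline or analysis. Nothing can be inferred about it either way, so the point is confined to the 10.1.3 tables.
- The Day 0 reference follows Protocol 12.5.2, which uses randomization/enrollment. That is true, and it is why the Day 0 tables should stay.
- The renal syndrome arose in patients who also received conditioning and donor marrow. The protocol reports no renal dysfunction in other siplizumab populations, including 13 renal transplant patients in MI-CP027. This lowers the expected frequency, but Protocol 4.5.4 still commits to following creatinine for renal injury.

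**Conclusion.** The point holds for the specified 10.1.3 tables. For creatinine and BUN they measure change and shift from a pre-transplant or Day 0 value, and they do not reliably show a within-subject post-transplant rise by arm. The eGFR change from Week 4 does not fill the gap for Days 10 to 20.

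How often the sign is wrong depends on a quantity that the documents do not give. Under the stated assumptions (uniform peaks over the documented range; pre-transplant means of 6, 8 and 10 mg/dL), about 21%, 38% and 53% of peaks read as a fall. The other 79%, 62% and 47% read as a rise of understated size.

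Two stronger readings are tempting and not supported. One is that post-transplant injury is generally tabulated as improvement: at two of the three assumed means, most peaks of the documented size still show as a rise. The other is that the shift table must show no shift: that follows only for a single high cut-off, and the criteria are not in the available text.

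This is a worthwhile, inexpensive improvement to a primary-endpoint summary. It does not mean that the plan would miss renal injury.

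**What to change.** Keep the Day 0 tables. In SAP 8.2 and 10.1.3, add for serum creatinine and BUN a summary by arm of each subject's maximum rise from the lowest prior post-transplant value. Give it as an absolute difference and as a ratio (for example, counts at ≥1.5 and ≥2), separately for transplant to Week 4 and Week 4 to Month 12. Base the creatinine shift table on the same post-transplant reference, and state the clinically notable criteria it uses. Extending the Week 4 eGFR baseline to creatinine would not serve, because it falls after the early window.

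Use scheduled-visit samples only. Daily in-hospital sampling makes the number of values depend on length of stay, and a minimum over more samples is lower by chance.

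The cost is SAP wording and modest programming on data already collected. There are two downsides. A running minimum yields some chance rises; the scheduled-visit restriction limits any arm difference due to length of stay but does not remove the chance rises. The restriction also means that a short peak between scheduled visits is seen only in the listings, which should therefore keep unscheduled samples.

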#### **10.1.4. Vital Signs**

All vital sign data will be listed by treatment, subject, and visit/time and if ranges are available, abnormalities will be flagged. Summary statistics and change from baseline will be provided by treatment and visit/time. Shift tables describing changes from baseline based on the clinically notable criteria will be presented.

#### **10.1.5. Physical Exam**

Physical exam data for each subject will be presented in a listing, if it is available.

#### **10.1.6. Graft Loss**

Graft Loss data will be summarized by group. If the subject undergoes allograft nephrectomy prior to starting permanent dialysis, then the day of nephrectomy is the day of graft loss.

#### **10.1.7. Death**

Primary cause of death will be summarized by treatment arm, and death data will be presented in a listing.

### **10.2. Pharmacokinetics and Pharmacodynamics**

#### **10.2.1. Pharmacokinetics**

PK samples will be evaluated for the subjects in PK analysis set at all dose levels.

Sipilizumab concentrations will be determined by a validated ELISA method; the anticipated Lower Limit of Quantification (LLOQ) is 10 ng/mL and concentrations will be expressed in mass per volume units. Concentrations below the LLOQ will be reported as “zero” and missing data will be labeled as such in the Bioanalytical Data Report.

The following PK parameters will be determined using the actual recorded sampling times and non-compartmental method(s):  $C_{max}$ ,  $T_{max}$ , area under the curve (AUC) last,  $AUC_{inf}$ ,  $T_{1/2}$ ,  $V_z/F$ , and  $CL/F$  from the serum concentration-time data.

The linear trapezoidal rule will be used for (AUC) calculation. Regression analysis of the terminal plasma elimination phase for the determination of  $T_{1/2}$  will include at least 3 data points after  $C_{max}$ . If the adjusted  $R^2$  value of the regression analysis of the terminal phase will be less than 0.75, no values will be reported for  $T_{1/2}$ ,  $AUC_{inf}$ , and  $CL$ .

Sipilizumab serum concentration data will be listed by treatment, subject, and visit/sampling time point. Descriptive summary statistics will be provided by treatment and visit/sampling time point, including the frequency (n, %) of concentrations below the LLOQ and reported as zero.

Summary statistics will include mean (arithmetic and geometric), SD, CV (arithmetic and geometric), median, minimum, and maximum. Concentrations below LLOQ will be treated as zero in summary statistics and for PK parameter calculations. A geometric mean will not be reported if the dataset includes zero values.

**Table 9-1 Non-compartmental pharmacokinetic parameters**

$AUC_{last}$	The AUC from time zero to the last measurable concentration sampling time ( $t_{last}$ ) (mass x time x volume-1)
$AUC_{inf}$	The AUC from time zero to infinity (mass x time x volume-1)
$AUC_{tau}$	The AUC calculated to the end of a dosing interval ( $\tau$ ) at steady-state (amount x time x volume-1)

$C_{max}$	The maximum (peak) observed plasma, blood, serum, or other body fluid drug concentration after single dose administration (mass x volume-1)
$T_{max}$	The time to reach maximum (peak) plasma, blood, serum, or other body fluid drug concentration after single dose administration (time)
$\Lambda_z$	Smallest (slowest) disposition (hybrid) rate constant (time-1) may also be used for terminal elimination rate constant (time-1)
$T_{1/2}$	The elimination half-life associated with the terminal slope ( $\Lambda_z$ ) of a semi logarithmic concentration-time curve (time). Use qualifier for other half-lives
$CL/F$	The total body clearance of drug from the plasma (volume x time-1)
$V_z/F$	The apparent volume of distribution during terminal phase (associated with $\Lambda_z$ ) (volume)

All calculated PK parameters will be listed by treatment and subject. Concentrations below the limit of quantification will not be considered for the calculation of PK parameters. Descriptive summary statistics will include mean (arithmetic and geometric), SD, and CV (arithmetic and geometric), median, minimum, and maximum. An exception to this is  $T_{max}$  where median, minimum and maximum will be presented.

A dose-independent, model-based analysis of the dose/concentration-exposure relationship should be derived using the same approach as the initial model used for expected concentration in the protocol. Such analysis may be reported in a separate standalone report.

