# 2 Objectives and Endpoints

Table 2-1 Objectives and Related Endpoints

Objective(s)	Endpoint(s)	
Primary Objective	Endpoints for primary objective	
To assess the safety, tolerability, PK and PD of siplizumab compared to rATG, in de novo renal transplant recipients at 12 months post-transplant.	
 
Adverse events
 
Serious adverse events
 
Clinically significant changes in clinical chemistry, hematology, vital signs, serology
 
siplizumab PK
 
Immunophenotyping
 
CD2 RO
 
eGFR via MDRD
 
	

 
Secondary Objectives
 
To measure changes in peripheral lymphocyte immunophenotype
 
To measure the time-course and duration of siplizumab induced lymphocyte depletion and time to recovery
 
To measure peripheral CD2-receptor occupancy following siplizumab administration over time
 
To assess the incidence of treated biopsy proven acute rejection (tBPAR) at 12 months
 
To assess the incidence of treatment emergent de novo, donor specific antibodies (DSA) at 12 months
 
To assess the incidence of antibody meditated rejection at 12 months
 
To assess repail function via eGER using MDRD equation at
 
	
 
Endpoints for secondary objectives
 
Immunophenotyping via FACS
 
Lymphocyte counts
 
CD2 RO
 
Anti-siplizumab Ab
 
Incidence of BPAR
 
de novo-DSA / anti-HLA antibody measurement
 
incidence of AMR
 
	

 
To assess renal function via eGFR using MDRD equation at Months 3, 6, 12 or EOS
 
		

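### SAP 10.2.1 and protocol 12.5.3 each both zero and exclude BLQ concentrations for PK parameters; the choice changes AUC when a sample between the two doses is BLQ

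*SAP*

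**What the plan says.** SAP 10.2.1 gives an LLOQ ("the anticipated Lower Limit of Quantification (LLOQ) is 10 ng/mL") and a reporting convention: "Concentrations below the LLOQ will be reported as “zero” and missing data will be labeled as such in the Bioanalytical Data Report". It then gives two instructions for the derived parameters.

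- In the paragraph on summary statistics: "Concentrations below LLOQ will be treated as zero in summary statistics and for PK parameter calculations".
- In the paragraph after Table 9-1: "Concentrations below the limit of quantification will not be considered for the calculation of PK parameters".

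Protocol 12.5.3 contains the same two sentences. Neither document limits either sentence to a sample position (pre-dose, between doses, trailing) or to a parameter (AUC or the terminal slope).

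Two further rules bear on the effect. The first is the integration method: "The linear trapezoidal rule will be used for (AUC) calculation". The second is the definition of AUClast in Table 9-1: "The AUC from time zero to the last measurable concentration sampling time". Half-life needs at least three points after Cmax. The objectives tables in SAP 4.1 and protocol section 2 list siplizumab PK under the primary objective.

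**The concern.** One BLQ value cannot be both a zero in the AUC and absent from it, so the analyst must choose. The SAP exists to make that choice before the data are seen. The laboratory delivers BLQ results as zero, so doing nothing applies one rule and a filter step applies the other. The reported tables would not show which was used.

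The choice could matter at the lower dose. Siplizumab is given on Days 0 and 4, with PK samples on Days 2 and 3 and before the Day 4 infusion. Protocol 4.1 expects enhanced clearance after the first dose, and protocol 1.1.4.5 describes very rapid clearance at low concentrations. If a fast-clearing subject is BLQ before the second dose, AUClast depends on the rule. So do AUCinf, CL/F and Vz/F where a terminal phase can be estimated. With 8 subjects per siplizumab arm, one or two such profiles can move an arm summary, and the results are meant to inform later dose and regimen selection.

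**Working it through.** The plan gives no figure to reproduce. The check has three parts.

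**1. Which outputs depend on the rule**

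- Cmax and Tmax: no, because a BLQ value is never the peak.
- Terminal slope: no, because zero has no logarithm. BLQ values have to be left out.
- Trailing BLQ values: no, because AUClast stops at the last measurable concentration.
- Day 0 pre-dose: trivially. Dropping it loses the first trapezoid, C(1 h)/48 in µg·day/mL.
- BLQ between the doses: yes.

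**2. Size of the jump for a BLQ value between doses**

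Time is in days, and the peak Cp is sampled 1 h after the start of the Day 4 infusion.

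If only the Day 4 pre-dose value is BLQ:

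- Zero rule: C3/2 + Cp/48.
- Exclusion: (25/24)(C3 + Cp)/2.
- Difference: C3/48 + Cp/2.

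If Day 3 is also BLQ, the line runs from Day 2 and the difference is (25/48)·C2 + Cp. Exclusion therefore adds roughly half the second-dose peak, or roughly the whole of it, times one day.

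**3. Illustration at 0.2 mg/kg**

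- From the protocol: one compartment with linear plus Michaelis-Menten elimination, KM 0.34 µg/mL, half-life 8.5 days, 1-hour infusions, the Appendix 1 sampling times, and LLOQ 0.010 µg/mL.
- Assumed: V 0.05 or 0.10 L/kg, and Vmax as shown.
- AUClast is taken from the first dose across both doses. Exclusion drops every BLQ value, including Day 0 pre-dose.
- First-day half-life = 23 × ln 2 / ln(C1h/C24h).

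| V (L/kg) | Vmax (µg/mL/day) | First-day half-life (h) | Day 3 (µg/mL) | Day 4 pre-dose (µg/mL) | Cp (µg/mL) | AUClast, zero | AUClast, excluded | Change |
|---|---|---|---|---|---|---|---|---|
| 0.05 | 0.6 | 70.6 | 1.726 | 1.128 | 5.095 | 21.208 | 21.125 | −0.4% |
| 0.10 | 0.6 | 43.5 | 0.399 | 0.131 | 2.109 | 7.444 | 7.402 | −0.6% |
| 0.05 | 1.5 | 32.1 | 0.138 | BLQ | 3.947 | 11.484 | 13.378 | +16.5% |
| 0.10 | 1.0 | 26.2 | 0.043 | BLQ | 1.971 | 5.344 | 6.290 | +17.7% |
| 0.05 | 2.1 | 22.1 | BLQ | BLQ | 3.925 | 4.978 | 8.983 | +80.4% |
| 0.10 | 1.2 | 21.3 | BLQ | BLQ | 1.963 | 2.501 | 4.524 | +80.9% |

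Hand check of row 3: 0.138/48 + 3.947/2 = 1.976. Subtract the lost first trapezoid, 3.944/48 = 0.082, to get 1.894. Then 11.484 + 1.894 = 13.378.

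Day 4 pre-dose first becomes BLQ at a Vmax between 1.35 and 1.40 (V = 0.05) or between 0.85 and 0.90 (V = 0.10). Day 3 joins it at a first-day half-life of about 25 h (V = 0.05) or 21 h (V = 0.10), so the border between the two patterns depends on volume.

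**Terminal phase.** After the second peak come the 3 h, 6 h and Day 7 samples. In rows 3 and 4 Day 7 is measurable (0.139 and 0.043 µg/mL), so the three-point minimum is met. A 16.5% to 17.7% higher AUC means CL/F lower by 1 − 1/1.165 = 14% to 1 − 1/1.177 = 15%, before the extrapolated tail is added. In rows 5 and 6 Day 7 is BLQ and two points remain. No half-life, AUCinf or CL/F can be derived there, and only AUClast is affected.

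**Purely linear elimination.** Day 4 pre-dose is BLQ if the half-life is below about 96 × ln 2 / ln(C0/0.010).

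- V = 0.05: C0 = 0.2/0.05 = 4 µg/mL, giving 66.5/ln 400 = 11.1 h.
- V = 0.10: C0 = 2 µg/mL, giving 66.5/ln 200 = 12.6 h.

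At 14 h the pre-dose value is about 35 or 18 ng/mL, both measurable, and the rules agree apart from the Day 0 pre-dose sample (about 1%).

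**The case against.** The strongest reply is that the conflict may never affect a result. Protocol 1.1.4.5 gives an 8.5-day half-life in renal transplant patients. Protocol 1.1.4.6 gives 14 to 49 h at 0.06 and 0.12 mg/kg, both below this trial's lowest dose. Under linear elimination the rules differ only at half-lives shorter than any of these. Protocol 4.1 predicts peaks above the concentration at which clearance accelerates, at both doses. With Vmax of 0.6 µg/mL/day or less, no sample between doses is BLQ.

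That stands as a limit on size, but it does not show that there is no effect. The protocol's own model is not linear. With its KM, BLQ values before the second dose appear at first-day half-lives inside the 14 to 49 h band, given a high enough Vmax. The documents as published give neither V nor Vmax, so this can be neither confirmed nor ruled out.

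A charitable reading would apply zero to AUC and exclusion to the terminal slope. That is workable, but neither sentence says it.

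A reader might infer more than the documents support:

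- **That the trial's primary conclusion is at risk.** Siplizumab PK sits under the primary objective, but protocol 12.4.1 names only safety data as primary endpoints. Protocol 12.5.3 places the PK analysis under secondary endpoints, and SAP 8.0 makes the analysis descriptive with no hypothesis test.
- **That the protocol predicts BLQ values between the doses.** The remark in protocol 6.2.8 about unquantifiable concentrations is a contingency for the escalation review at about 28 days after dosing.
- **That CL/F and Vz/F are distorted as much as AUClast in the worst cases.** In those cases no terminal phase can be fitted.

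**Conclusion.** The contradiction is certain: two incompatible instructions for the same calculation, in one SAP section and again in one protocol section. Its reach is narrow. It bears on AUClast, and on AUCinf, CL/F and Vz/F where a terminal phase can be estimated, when a sample between the two doses is BLQ.

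The size is conditional. At 0.2 mg/kg it runs from nothing of note to about +17% to +18% with one BLQ sample between doses and about +80% with two. These figures rest on assumed V (0.05 to 0.10 L/kg) and assumed Vmax. They also rest on reading AUClast as running from the first dose across both. They are illustrations and do not forecast this trial. The point should be corrected because the repair is cheap and the choice should not be made after seeing the profiles. It does not threaten the trial's main conclusions.

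**What to change.** In SAP 10.2.1:

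1. In the sentence that sets BLQ values to zero, strike only the closing clause that extends the rule to PK parameters. Keep zero for concentration summary statistics. That part is not in conflict, and the next sentence, on geometric means, relies on it. Deleting the whole sentence would leave concentration summaries without a rule.
2. Replace the BLQ sentence after Table 9-1 with one rule by position:
   - before the first dose, BLQ = 0;
   - any BLQ between the first and second dose, including Day 3 and Day 4 pre-dose, = 0 for AUC;
   - after the last measurable concentration, BLQ is excluded;
   - BLQ values are never used in the terminal-slope regression.
3. State that this rule supersedes protocol 12.5.3, which otherwise stays contradictory.

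The cost is a few lines in the SAP and one setting in the non-compartmental program, with no new data. It should be done before database lock. If lock has passed, the clinical study report should state which rule was run and give AUC both ways for any subject with a BLQ sample between the doses.
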